## 1 Program Summary

This study conducted a retrospective analysis of 64 patients with mild cognitive impairment of the kidney deficiency phlegm and stasis type who underwent treatment with Naohuan Dan combined with Idebenone. The patients' cognitive function was evaluated using the Mini-Mental State Examination (MMSE) and the Montreal Cognitive Assessment (MoCA) before and after treatment. Daily living abilities were assessed using the Activities of Daily Living (ADL) scale, depression status was evaluated using the Geriatric Depression Scale (GDS), and the severity of Traditional Chinese Medicine (TCM) syndrome was assessed using the TCM diagnostic scale. Peripheral blood from the patients was also collected for analysis of neuron-specific enolase (NSE) and inflammatory factors. The aim was to evaluate the safety and feasibility of using Naohuan Dan combined with Idebenone for the treatment of mild cognitive impairment of the kidney deficiency phlegm and stasis type.

## 2 Introduction

Mild cognitive impairment (MCI), a transitional state between aging and dementia, is clinically characterized by a decline in cognitive function, but daily living abilities remain unaffected or mildly impaired. Previous studies have shown that 50% of MCI patients will progress to dementia within 3-4 years of onset, and the proportion of individuals progressing to dementia increases with age and disease duration. The exact pathogenesis of MCI is not yet fully understood, and there is a lack of effective clinical treatments. Cognitive impairment in MCI patients can severely impact their quality of life and burden families and society.

MCI can be divided into amnestic and non-amnestic types, with amnestic MCI mainly characterized by memory impairment and non-amnestic MCI mainly characterized by cognitive impairments such as language, visual-spatial recognition, and executive function. Main neurological and psychiatric symptoms include anxiety, depression, apathy, and sleep disturbances. A meta-analysis using a random-effects model showed that the cumulative incidence rate of dementia for MCI

patients aged 65 and above after 2 years was 14.9%. As the aging of the population accelerates in China and life expectancy gradually increases, the incidence rate of MCI is on the rise.

MCI belongs to the category of "forgetfulness", "fondness for remembering", and "dementia" in traditional Chinese medicine, with the pathological basis of marrow decline, brain consumption, and loss of function of the nerve machinery. It is a syndrome of virtual and actual deficiency, and the condition is complex. At present, there are several single herbs in traditional Chinese medicine that can improve mild cognitive impairment (MCI), such as ginkgo biloba, acorus calamus, ginseng, and polygala, which have effects on inhibiting neuronal apoptosis, promoting neuronal metabolism, and reducing amyloid deposition, thereby improving cognitive function. A meta-analysis found that oral administration of Ginkgo biloba leaf extract preparations for MCI treatment is clinically effective and can effectively prevent the incidence of dementia, but its safety still needs further exploration. In addition, single herbs have the drawback of having a single target point and cannot effectively improve cognitive function in MCI. Chinese medicine compound formulas have multi-target pharmacological effects and multi-level actions. Haifeng Wang found that the TCM for invigorating the kidney and activating blood circulation, which is composed of several Chinese herbs, can improve the executive function and memory of MCI patients, and its mechanism of action may be related to strengthening the body's ability to resist oxidative stress and reducing the damage of free radicals to neurons. Lijing Yang found that the Chuanpu Yizhi Tang compound formula can reduce the levels of serum Hcy and AchE, improve the cognitive function and daily life ability of MCI patients, and has good clinical efficacy. In addition, traditional Chinese medicine techniques such as acupuncture, traditional exercises, and massage have shown certain efficacy in treating MCI, which is worth further exploration and promotion.

Based on the above research background, we believe that the combination of Naohuan Dan combined with Idebenone has great application prospects for the treatment of Kidney Deficiency Phlegm Stagnation Type MCI. To this end, we have

designed a clinical study to evaluate the efficacy and safety of the combination of Naohuan Dan combined with Idebenone for the treatment of MCI, by assessing relevant cognitive function rating scales and TCM syndrome scores. This study aims to provide valuable information for the integration of TCM and Western medicine in the treatment of MCI.

### **3 Research Objectives and Endpoints**

#### **3.1 Main purpose**

This study evaluated the efficacy of Naohuan Dan combined with Idebenone for treating MCI patients with Kidney-Deficient and Phlegm-Stasis syndrome. Changes in cognitive function, daily living abilities, depression levels, and Traditional Chinese Medicine clinical symptoms were assessed using relevant rating scales, and compared with the efficacy of Idebenone alone, demonstrating the advantages of combining traditional Chinese and Western medicine in treatment.

#### **3.2 Main outcome**

The primary outcome measure for the study was the Mini-Mental State Examination (MMSE) scale scores [9], which were used to examine the cognitive function of the participants before and after therapy. A total score of 23-30 is considered to indicate normal cognitive function, 17-22 indicates mild cognitive impairment, 11-16 indicates moderate cognitive impairment, and 10 or below indicates severe cognitive impairment.

The clinical efficacy was evaluated based on the MMSE scale, and the efficacy was calculated by comparing the scores before and after the therapy. The following criteria were used to determine the efficacy: (i) Markedly effective:  $\geq 20\%$  improvement in MMSE score. (ii) Effective rate:  $\geq 12\%$  improvement in MMSE score. (iii) Ineffective:  $< 12\%$  improvement in MMSE score. The total efficacy was calculated as the sum of the markedly effective and effective rates.

### **3.3 Secondary outcomes**

The secondary outcome measures for the study included various scales and serological indicators. The scales used in the study were the Montreal Cognitive Assessment (MoCA) scale, the ADL scale, the Geriatric Depression Scale (GDS) and the TCM syndrome score scale.

The MoCA scale is a widely used screening tool for detecting mild cognitive impairment. It assesses various cognitive domains such as attention, memory, visuospatial skills, language, and orientation. The total score on the MoCA scale is 30, and a score of 26 or higher is considered to indicate normal cognitive function.

The ADL scale is used to assess the participants' ability to perform daily living activities. The total score on the ADL scale is 100 points.

The GDS scale is a self-report assessment tool used to detect and measure the severity of depression in older adults. The total score on the GDS scale is 30 points.

The TCM clinical symptoms of the participants were evaluated using the TCM syndrome score scale. This tool assesses the severity of specific TCM symptoms and divides them into four grades: none, mild, moderate, and severe, with 0, 2, 4, and 6 points (for main symptoms) or 0, 1, 2, and 3 points (for secondary symptoms), respectively. The total score was calculated before and after the therapy to determine the effectiveness of the treatment.

Blood samples were collected from the participants before and after the therapy via cubital venipuncture. Enzyme-linked immunosorbent assay (ELISA) was used to determine the serum levels of neuron-specific enolase (NSE), interleukin-8 (IL-8) and tumor necrosis factor-alpha (TNF- $\alpha$ ) using the Reader M3 multi-function microplate reader.

### **3.4 Safety Index**

Before and after treatment, the patient's elbow vein blood is collected for blood routine, urine routine, stool routine, and liver and kidney function tests. The patient's electrocardiogram is also monitored, and any adverse reactions after medication are observed and treated accordingly.

## **4 Research Population**

### **4.1 Inclusion criteria**

The following inclusion criteria were used: (1) diagnosis in line with Chinese medicine and Western medicine; (2) suitable for age 55-85 years old, gender is not limited; (3) a score between 21-26 on Mini-Mental State Examination (MMSE), 1 point for primary school education; (4) agree to take part in this experiment and sign the informed consent form.

### **4.2 Exclusion criteria**

The following exclusion criteria were used: (1) patients with severely impaired heart, liver, kidney and other functions; (2) patients with neurological diseases that affect brain function and cognitive impairment; (3) patients with severe depression and mental illness; (4) patients with poor compliance and cooperation who failed to complete the study according to the protocol.

### **4.3 Lifestyle and Precautions**

During the course of treatment, if the patient has comorbidities such as hypertension, diabetes and hyperlipidemia, their original treatment plan should be maintained, and appropriate symptom-relieving treatments such as blood pressure-lowering, hypoglycemic and lipid-lowering drugs should be provided. Smoking and drinking should be prohibited during the treatment period, and regular exercise and a light diet should be maintained.

### **4.4 Recruitment and Retention Strategies**

At the outpatient and ward departments of Traditional Chinese Medicine and Rehabilitation of Sun Yat-sen Memorial Hospital, eligible MCI patients with the type of kidney deficiency and phlegm stasis were identified according to the inclusion criteria. After fully communicating trial-related information with the patients, they

[figure not shown]
were informed of the possible adverse reactions and risks, and asked to sign an informed consent form voluntarily and informed about the trial plan.

Retention strategies: (1) Researchers should maintain one-on-one communication with patients as much as possible. (2) Clear trial-related information should be provided to patients during the first communication, along with a process calendar, and patients should be informed of the next appointment time and reminded through phone calls. (3) Researchers can communicate the current progress with patients at appropriate times to help them fully recognize their contribution to the research. (4) Sufficient work should be done to obtain informed consent during the screening phase and to answer any questions patients may have.

## **5 Research Design**

### **5.1 Intervention**

This retrospective, two-armed, single-center clinical observation evaluates the combination of Naohuan Dan and Idebenone for the treatment of MCI patients with Kidney Deficiency and Phlegm Stasis. Eligible patients were randomized using a random number table into a control group and a treatment group. The control group was given 30mg of Idebenone tablets three times a day after meals, while the treatment group was given Naohuan Dan in addition to Idebenone. The main components of the Naohuan Dan formula are Rehmannia glutinosa 25g, Codonopsis pilosula 20g, Acorus calamus 10g, Polygala tenuifolia 8g, Eucommia ulmoides 15g, and Poria cocos 12g, among other ingredients. The herbal granules were provided by Yifang Pharmaceutical Co., Ltd. The patients in both groups received corresponding treatments for underlying diseases such as hypertension and diabetes if present. One dose of herbal granules was administered daily with warm water in the morning and evening.

**Fig. 1** CONSORT flow chart.

## 5.2 Research Calendar

The scale	MMSE	√															√
The MoCA scale		√															√
The ADL scale		√															√
The GDS scale		√															√
The TCM Syndrome score scale		√															√
Lab Test		√															√
Blood routine, Urine routine, Stool routine and Liver and Kidney function		√															√
Electrocardiogram		√															√
Adverse Events and Evaluation		√	√	√	√	√	√	√	√	√	√	√	√	√	√	√	√
Complete the Case Report Form		√	√	√	√	√	√	√	√	√	√	√	√	√	√	√	√

### 5.3 Definition of End of Study

When the last patient who met the inclusion and exclusion criteria completed the prescribed course of drug treatment, there were no obvious adverse reactions and events in the last follow-up, and the corresponding data were collected as the end of the study.

### 5.4 Statistical Analysis

#### 5.4.1 sample size

This study is a retrospective, two-arm study with a fixed sample size and no strict hypothesis testing. A total of 64 participants were enrolled in this study.

#### 5.4.2 Data Analysis Set

Full Analysis Set (FAS) analyzed all cases who were enrolled and received at least

one dose of the study drug, according to the intention-to-treat (ITT) principle. For cases where the entire treatment process could not be observed, the last observed data was carried forward to the final results of the trial (LOCF).

Per-protocol Set (PPS) included all cases that complied with the trial protocol, had good compliance, did not use any prohibited medication during the trial, and completed the required case report form. No data imputation was conducted for missing data. The efficacy of the medication was analyzed for both FAS and PPS.

Safety Analysis Set (SAS) consisted of all enrolled cases who had received at least one dose of the study drug and had safety records available after medication use. This dataset was used for safety analysis.

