# **7 Study Intervention Discontinuation/Subject Discontinuation and Withdrawal**

## **7.1 Study Intervention Discontinuation**

The enrolled patients may discontinue treatment at any time for any reason or, in case of any adverse event, at the discretion of the investigator. Furthermore, the investigator may stop the treatment of a patient if the patient is deemed unsuitable for treatment, violates the study protocol, or for management and/or safety reasons.

The subject must discontinue treatment but may continue to be monitored in the

study if any of the following occur: 1) the patient or the patient's family requests discontinuation of treatment; 2) an intercurrent illness which interferes with further treatment occurs; 3) the investigator determines that the patient should be withdrawn from the study; 4) poor compliance by the patient; 5) the investigator believes that continuing to administer the investigational drug to the subject would place the subject at unnecessary risk based on the subject's medical condition or personal situation; 6) completion of the treatment as outlined in the protocol.

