## **7.2 Subject discontinuation/withdrawal from the study**

If a patient or their family withdraws their informed consent to participate in the study, the enrolled patient must be withdrawn from the study. If a patient withdraws from the study, they will no longer receive treatment or participate in planned visits. If a patient is lost to follow-up, they must also be withdrawn from the study.

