## **7.3 Lost to follow-up**

Timely education and reminders should be provided to enrolled patients. The next follow-up appointment should be scheduled during each visit, and the patient's contact information should be recorded to facilitate timely communication, enhance medication adherence and patient follow-up compliance, and reduce data loss due to patient loss to follow-up. If there is data loss due to patient loss to follow-up, it should be excluded from data analysis and appropriately documented.

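### A dosed patient lost to follow-up is kept in the FAS by section 5.4.2 and removed from analysis by section 7.3, and exclusion criterion 4.2(4) removes some non-completers as well

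*Protocol*

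**What the plan says.** - **Section 5.4.2, FAS.** All enrolled cases with at least one dose are analysed under the ITT principle. Where the whole course of treatment was not observed, "the last observed data was carried forward to the final results of the trial (LOCF".
- **Section 5.4.2, PPS.** This set "included all cases that complied with the trial protocol, had good compliance", used no prohibited medication and completed the case report form. The section adds: "No data imputation was conducted for missing data. The efficacy of the medication was analyzed for both FAS and PPS".
- **Section 7.3.** "If there is data loss due to patient loss to follow-up, it should be excluded from data analysis and appropriately documented". No analysis set is named.
- **Section 7.2.** "If a patient is lost to follow-up, they must also be withdrawn from the study". Also: "If a patient withdraws from the study, they will no longer receive treatment or participate in planned visits".
- **Section 4.2, criterion (4).** Excluded are "patients with poor compliance and cooperation who failed to complete the study according to the protocol".
- **Sections 3.2 and 5.2.** MMSE, the primary outcome, is scored before and after therapy; the calendar ticks it only in its first and last columns. A gain of at least 12% is Effective, at least 20% Markedly effective, and anything less than 12% Ineffective.
- **Section 4.1.** Baseline MMSE lies between 21 and 26.

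**The concern.** Two sections of one protocol give opposite instructions for the same patient. An analyst following 5.4.2 counts a dosed, lost patient in the denominator with an imputed score. An analyst following 7.3 leaves that patient out. Because efficacy is analysed in the FAS, this decides who counts in the primary result.

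Criterion 4.2(4) adds a related problem. Whether a patient completes cannot be known at entry, so as an eligibility rule it would remove patients already randomised and dosed, whom the ITT-based FAS is meant to keep.

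The LOCF rule also does something the protocol does not state. With no MMSE between baseline and the end, a lost patient has no later score to carry forward.

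**Working it through.** **1. Which rule covers whom**

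| Patient (enrolled and dosed) | 5.4.2 FAS | 7.3 | 4.2(4) |
|---|---|---|---|
| Lost to follow-up | keep, LOCF | exclude | silent, unless also a poor complier |
| Poor complier who did not complete | keep, LOCF if no final score | silent, unless also lost | exclude |
| Stops or withdraws for another reason, e.g. "an intercurrent illness which interferes with further treatment occurs" (7.1) | keep, LOCF if no final score | silent | silent |

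The first two rows each contain a contradiction. The groups overlap only in part. Under 7.1 a patient who stops treatment may still be monitored, and so may have a real final score that needs no imputation.

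**2. What LOCF does to a lost patient**

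By 7.2 a lost patient is withdrawn, and a withdrawn patient attends no further planned visits. Only the baseline MMSE exists, so the imputed change is 0. The 12% threshold is 0.12 x 21 = 2.52 at the lowest baseline, 0.12 x 25 = 3.00, and 0.12 x 26 = 3.12 at the highest. Effective therefore needs a gain of 3 points at baselines 21 to 25 and 4 points at 26. A change of 0 is always Ineffective.

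**3. Size in general**

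The protocol gives no figure to reproduce: 5.4.1 states a fixed 64 and no dropout rate. For one arm, let n be its FAS, l the number lost without a final score, and s the responders among the rest (or S their summed MMSE change).

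- 5.4.2: s/n, or S/n
- 7.3: s/(n-l), or S/(n-l)
- Ratio of 7.3 to 5.4.2: n/(n-l) = 1/(1-d), with d = l/n

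This gives x1.00 at d = 0, 1/0.95 = x1.05 at 5%, 1/0.90 = x1.11 at 10% and 1/0.80 = x1.25 at 20%. It needs no assumption about the treatment effect or the reason for loss.

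**4. Illustration**

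Assumed, not in the protocol: 32 per arm, and 18 (treatment) v 11 (control) responders among patients with a final score. Under LOCF the result is 18/32 v 11/32 = 56.3% v 34.4%, whatever the losses. The test is Pearson chi-square, with the continuity-corrected p-value in brackets.

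| Lost, treatment/control | Proportions under exclusion | p (corrected) |
|---|---|---|
| 0/0 (same as LOCF) | 18/32 v 11/32 | 0.079 (0.132) |
| 2/2 | 18/30 v 11/30 | 0.071 (0.121) |
| 4/4 | 18/28 v 11/28 | 0.061 (0.109) |
| 6/6 | 18/26 v 11/26 | 0.051 (0.094) |
| 4/2 | 18/28 v 11/30 | 0.036 (0.066) |
| 6/2 | 18/26 v 11/30 | 0.015 (0.030) |
| 2/6 | 18/30 v 11/26 | 0.186 (0.292) |

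Equal losses do not cross 0.05 here. Losses of 4/2 cross only without correction, and 6/2 cross with or without it. With 2/6, exclusion gives the larger p-value.

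**5. Neither rule is right by construction**

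Take losses of 4/2 and suppose 2 of the 4 and 1 of the 2 would have responded.

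- Truth: 20/32 v 12/32 = 62.5% v 37.5%, difference 25.0 points
- LOCF: 18/32 v 11/32, difference 21.9 points
- Exclusion: 18/28 v 11/30 = 64.3% v 36.7%, difference 27.6 points

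**The case against.** **The sections can be reconciled.** Section 7.3 is about retention, while 5.4.2 is where the analysis sets are defined. One could take 7.3 to exclude only the missing values, or to describe the PPS alone. Neither reading removes the problem. If only missing values are excluded, 7.3 still forbids the imputation that 5.4.2 orders. If 7.3 means the PPS, it does not say so, and it repeats what 5.4.2 already settles there. What stands is that the PPS-only reading is a natural intention, which makes the repair easy.

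**The study is called retrospective.** Sections 1 and 5.4.1 use that word. If 4.2(4) only selected records and all 64 patients completed, nothing conflicts in practice. That is possible, but sections 4.4 and 5.1 describe consent and randomisation, which point to prospective enrolment.

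**The size is uncertain.** The 1/(1-d) ratio does not apply to mean final score. With an assumed baseline of 23.5, a gain of 3 and d = 12.5%, LOCF gives 23.5 + 3 x 28/32 = 26.125 against 26.5, a ratio of only x1.014. The p-value example also starts close to 0.05. With 4/2 lost, 18 v 12 responders gives 0.064 uncorrected under exclusion and 16 v 11 gives 0.118, so neither crosses. Section 5.4.1 itself disclaims strict hypothesis testing. All of this stands as a limit on the illustration. It does not touch the contradiction.

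**The sensitivity model is SAP-level detail.** That is fair. The two wording changes to 7.3 and 4.2 carry the repair.

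**Conclusion.** The concern holds. As written, the protocol lets a dosed patient lost to follow-up be counted in the FAS as change 0 and Ineffective, or be left out. Criterion 4.2(4) likewise removes poor compliers who did not complete although the FAS keeps them.

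For responder rate and mean MMSE change the two treatments of lost patients differ within an arm by exactly 1/(1-d). The effect on the comparison between arms depends on how many are lost in each arm and who they are, which the protocol does not give. It can go in either direction, and it is nil if nobody was lost. The p-values rest on the assumed arm sizes and responder counts and show only that the choice of rule can matter. Because the ambiguity concerns who is analysed for the primary outcome, it must be resolved.

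**What to change.** 1. **Section 4.2:** delete criterion (4) as far as it concerns non-completion, and use non-completion only to define the PPS, which already requires good compliance.
2. **Section 7.3:** state that the exclusion applies to the PPS only, so that the FAS keeps all randomised, dosed patients.
3. **Section 5.4.2:** say that for a patient without a final score the FAS imputation is baseline carried forward. Beside it, report a baseline-adjusted analysis of observed final MMSE scores as a sensitivity analysis. This item is useful but secondary to the first two.

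**Cost:** wording in three sections and one extra model, with no new patients, visits or tests. The FAS figure may be less favourable than one that leaves lost patients out. If 4.2(4) has already been applied to enrolled patients, their records must be restored to the FAS or their exclusion reported, and the stated 64 may change. Patients without a final score still have none, so neither analysis removes the uncertainty about them.
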